Appendix 3. Clinical Laboratory Assessments

Hematology:
 
Erythrocytes Hemoglobin Hematocrit Platelets Total leukocytes and differential (neutrophils, lymphocytes, monocytes, eosinophils, basophils)
	
Liver Tests:
 
Total bilirubin (reflex direct [conjugated] bilirubin) AST ALT Alkaline phosphatase Prothrombin time, INR Alpha-1 antitrypsin and protease inhibitor (PI) typing

Chemistry:
 
Creatine phosphokinase Lactic dehydrogenase (LDH) Creatinine and calculated creatinine clearance Albumin Glucose Serum amylase Lipase (if serum amylase is $\geq 1.5 \times$ ULN) α-fetoprotein (Screening Visit) Blood urea nitrogen (BUN) Uric acid Total iron (Screening Visit)
	
Urinalysis:
 
Protein Blood Glucose
 
Urine Pregnancy Test:
 
Post-menarchal females only (reflex serum β-HCG if positive)

Electrolytes:
 
Sodium Potassium Bicarbonate Phosphorus+ Calcium Magnesium Chloride
	
HBV Serology:
 
HBsAg, HBeAg (reflex HBsAb and HBeAb).

Bone Biochemical Markers:	
 urine bicarbonate and n-telopeptide; serum c-telopeptides, osteocalcin, bone-specific alkaline phosphatase, PTH, and vitamin D levels (25-hydroxy) and 1,25 (dihydroxyvitamin) D levels; fasting serum creatinine/phosphate and urine creatinine (spot)/phosphate for measurement of the renal phosphate threshold (TmP/GFR) 	Virology: Plasma and serum for HBV DNA and serology HIV, HAV, HDV and HCV (Screening Visit) Viral genotyping (A–H), resistance surveillance
	Tenofovir DF Concentration: Plasma concentration	
Serum β-HCG Pregnancy Test:	Post-menarchal females only; at Screening, Baseline, Weeks 48, 72, 192, or Early Study Discontinuation/End of Treatment Visits; reflex if urine test positive at all other study visits	Storage: Plasma and serum for storage

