4.2. Inclusion Criteria

Subjects must meet *all* of the following inclusion criteria to be eligible for participation in this study.

- Male or female
- 2 years to < 12 years of age (consent of parent or legal guardian required)
- Body weight $\geq 10\text{kg}$
- Documented chronic HBV infection, defined as positive serum HBsAg ≥ 6 months
- HBeAg-positive or HBeAg-negative
- HBV DNA $\geq 10^5$ copies/mL (PCR method)
- ALT $\geq 1.5 \times \text{ULN}$ at screening
- Estimated glomerular filtration rate (creatinine clearance) $\geq 80 \text{ mL/min/1.73m}^2$

Estimated creatinine clearance using Schwartz Formula
(mL/min/1.73m^2) = $k \times L/\text{Scr}$

[(k is proportionality constant: pediatric males/females ≥ 2 years to < 12 years $k = 0.55$; for adolescent females ≥ 12 years old, $k = 0.55$, and for adolescent males ≥ 12 years, $k = 0.70$); L is height in centimeters (cm); and Scr is serum creatinine (mg/dL)]

- Adequate hematologic function (absolute neutrophil count $\geq 1,500/\text{mm}^3$; hemoglobin $\geq 10.0 \text{ g/dL}$)
- Negative serum β -HCG pregnancy test (for females of childbearing potential only)
- Male and female subjects of childbearing potential (defined in Section 7.7.1) identified as choosing to become sexually active must agree to utilize highly effective contraception methods or agree to abstain from heterosexual intercourse while on study treatment and for 30 days following the last dose of study drugs (refer to Section 7.7.2).

- Parent or legal guardian able to provide written informed consent prior to any screening evaluations and willing to comply with study requirements
- Subject able to provide written assent as determined by IRB/IEC/local requirements and Investigator's discretion.
- No prior tenofovir DF therapy (subjects may have received prior interferon-alfa and/or other oral anti-HBV nucleoside/nucleotide therapy; subjects must have discontinued interferon-alfa therapy ≥ 6 months prior to screening; subjects experienced on other anti-HBV nucleoside/nucleotide therapy must have discontinued therapy ≥ 16 weeks prior to screening to avoid flare if randomized to the placebo arm)

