 - Serum chemistry and liver function tests, including albumin, alkaline phosphatase, AST, ALT, total bilirubin (reflex to direct [conjugated] bilirubin if total bilirubin $> 1.5 \times$ ULN), bicarbonate, BUN, calcium, chloride, CPK, creatinine (and calculated creatinine clearance), glucose, LDH, magnesium, phosphorus, potassium, sodium, uric acid, and amylase (reflex lipase testing if total amylase is $\geq 1.5 \times$ ULN)
 - At Weeks 96, 144, and every 48 weeks during the Extension Phase: Serum bone biochemical markers, including serum c-telopeptides, osteocalcin, bone-specific alkaline phosphatase, PTH, vitamin D levels (25-hydroxy), 1,25 (dihydroxyvitamin) D levels, and fasting creatinine and fasting phosphate
 - Hepatitis B serology (HBeAg and HBsAg; reflex HBeAb and HBsAb if Ag negative) (Weeks 64, 72, 80, 96, and then every 12 weeks until the end of the study including the Extension Phase)
 - Plasma HBV DNA (PCR method)
 - Plasma for determination of tenofovir concentration
 - At Weeks 96 and 144: Serum for resistance surveillance
 - Serum and plasma for storage (for potential pharmacokinetic and/or virologic assays, including resistance surveillance, HBsAg and HBeAg quantification and compliance assessment)
- Urine samples for:
 - Urinalysis (protein, glucose, blood)
 - Urine pregnancy test (for females of childbearing potential only; positive urine pregnancy test will be immediately confirmed with a serum pregnancy test)
 - At Weeks 72, 96, 144, and every 48 weeks during the Extension Phase: Urine bone biomarkers, including urine bicarbonate, urine n-telopeptide, and spot urine creatinine and phosphate

- Weeks 72, 96, 144, and every 48 weeks during the Extension Phase: DEXA scan of spine and whole body (DEXA scan must be performed \pm 10 days from scheduled study visit)
- Review of AEs and concomitant medications
- Retrieval of study medication and assessment of medication adherence
- Study drug dispensing (including multivitamin) and instructions on appropriate dosing and administration
- At Week 56 only: Provide all subjects with a Subject Dosing Diary Card to complete the diary for 10 days prior to the next visit.
- At Week 64 only: Collect the Subject Dosing Diary Card completed by the subject daily for 10 days prior to these visits.

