7.7.1. Definition of Childbearing Potential

For the purposes of this study, a female subject of childbearing potential is a pubertal female regardless of whether or not she has had a menses (premenarchal, Tanner Stage 3). This also includes a female subject who has not had any of the following conditions or procedures considered very rare in this age group: hysterectomy, bilateral oophorectomy, or medically documented ovarian failure.

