7.7.2. Contraceptive Requirements

Male study subjects and female study subjects of childbearing potential who are not heterosexually active should have periodic confirmation of continued abstinence from heterosexual intercourse and regular pregnancy testing while taking tenofovir DF. Female study subjects of childbearing potential who have been identified during the study as choosing to become sexually active should be counseled appropriately on the protocol-recommended method(s) for avoiding pregnancy in case the subject chooses to continue with heterosexual intercourse.

Male and female subjects of childbearing potential who engage in heterosexual intercourse must either agree to use protocol-recommended method(s) of contraception or agree to abstain from heterosexual intercourse from the Screening/Enrollment Visit throughout the study period and for 30 days following the last dose of tenofovir DF. The investigator should identify those subjects at risk for becoming sexually active and provide counsel appropriately on the protocol-recommended method(s) for avoiding pregnancy during the trial. These methods are recommended due to the low failure rate (i.e., less than 1% per year). See [Table 7-1](#) for the protocol-recommended methods.

Female subjects of childbearing potential must have a negative serum pregnancy test at Screening and Baseline (Day 1) prior to receiving the first dose of study drug. Lactating females will not be enrolled in this study.

Table 7-1. Protocol-Recommended Contraceptive Methods

Single Methods	Combination Methods

Intra-uterine devices (IUDs)
 
 • Copper T 380A IUD • LNg 20 IUD 
Progesterone
 
 • Implant 	
Estrogen and Progesterone
 
 • Oral contraceptives plus barrier • Transdermal patch plus barrier • Vaginal ring plus barrier 
Progesterone
 
 • Injection plus barrier 
Barrier methods
 
 • Diaphragm • Cervical cap • Male condom

Other contraceptive methods may be acceptable after discussion with the Medical Monitor.

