- g HBeAg and HBsAg and, if negative, reflex HBeAb and HBsAb, respectively.
- h Determination of HBV viral genotype (A–H) will be performed at the Baseline Visit for all subjects. Resistance surveillance will be conducted at Baseline for all subjects, and attempted for all viremic subjects (HBV DNA \geq 400 copies/mL [69 IU/mL]) at Weeks 48, 96, 144, and 192, as well as at the Early Discontinuation Visit, if applicable.
- i Including estimated creatinine clearance, by the Schwartz Formula (2 to <12 years old).
- j PT/INR will be performed at the Screening and Baseline Visits, then as a reflex test in subjects experiencing exacerbation of hepatitis thereafter.
- k For females of childbearing potential only; a serum β -HCG pregnancy test will be performed at Screening, Baseline, Weeks 48, 72, 192 and Early Study Drug Discontinuation/End of Treatment Visit (if applicable). Urine pregnancy testing will be performed at all other study visits through the end of the study including the Extension Phase. A positive urine pregnancy test must be confirmed immediately with a serum pregnancy test.
- l Blood (serum and plasma) collected for long-term storage and possible future testing (e.g., pharmacokinetic and/or virologic analysis).
- m DEXA scan will be performed between the Screening and Baseline Visits, and must be performed prior to randomization and receipt of study drugs. All other DEXA scans must be performed within \pm 10 days of the scheduled study visits. DEXA scan will be performed at the time of switch for subjects switching from placebo to tenofovir DF, unless the most recent DEXA scan was performed within 12 weeks earlier.
- n Specimens for bone biochemical markers must be collected in the morning in a fasted state, or, if fasting is not feasible, within two hours of the time of day that the Baseline Visit specimen was collected. For example, if the bone biochemical markers were drawn at 7:00 AM for the Baseline Visit, they must be drawn no earlier than 5:00 AM and no later than 9:00 AM for Week 24, 48, 72, 96, and subsequent specified visits. Bone biochemical markers will also be collected at the time of switch for subjects switching from placebo to tenofovir DF if not done within 12 weeks prior to switch. Bone biochemical markers will also be collected at the Screening Visit; the mean of the Screening and Baseline Visit values will constitute the study baseline, to which subsequent values will be compared.

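### Protocol Appendix 3 limits pregnancy testing to post-menarchal girls, which contradicts the protocol's own definition of childbearing potential

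*Protocol*

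**What the plan says.** Appendix 3 has two pregnancy-test cells, and both restrict the population by menarche. The serum cell reads "Post-menarchal females only; at Screening, Baseline, Weeks 48, 72, 192, or Early Study Discontinuation/End of Treatment Visits". The urine cell opens "Post-menarchal females only (reflex serum".

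Section 7.7.1 sets the definition for the study: "a female subject of childbearing potential is a pubertal female regardless of whether or not she has had a menses (premenarchal, Tanner Stage 3").

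Every other place that states who is tested uses childbearing potential:

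- Section 4.2 makes a negative serum test an inclusion criterion: "pregnancy test (for females of childbearing potential only").
- Section 7.7.2 says: "Female subjects of childbearing potential must have a negative serum pregnancy test at Screening and Baseline", before the first dose. It also asks for regular testing on treatment in girls of childbearing potential who are not sexually active.
- The Section 6 visit lists use the same population. Sections 6.2.1 and 6.2.3 have "Urine pregnancy test (for females of childbearing potential only; positive urine pregnancy test will be immediately confirmed with a serum pregnancy test"); Sections 6.1.1, 6.1.2, 6.2.2 and 6.2.4 list a serum test.
- Appendix 2 footnote k begins "For females of childbearing potential only; a serum" and schedules that "pregnancy test will be performed at Screening, Baseline, Weeks 48, 72, 192 and Early Study Drug Discontinuation/End of Treatment Visit", with urine tests at the other visits.
- The Synopsis, Section 3 and SAP Section 1.2 also describe testing in females of childbearing potential.

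**The concern.** A premenarchal girl at Tanner Stage 3 is to be tested under Section 7.7.1 and must not be tested under Appendix 3. The wider definition is there to cover girls before their first menses, and Appendix 3 removes exactly that group. Nothing in the protocol reconciles the two rules or says which one governs.

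The stake is subject safety and compliance. Section 7.7 says the risks of tenofovir DF in pregnancy have not been evaluated in pregnant women. Pregnancy is an exclusion (Section 4.3) and a reason to stop study drug (Section 6.11). The group is plausible in this trial: entry age is 2 to under 12 years, SAP Section 6.4 records that some subjects were already 12 by baseline, and treatment runs to Week 192 with an Extension Phase after that. Younger girls can therefore enter puberty during follow-up.

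**Working it through.** **Comparing the rules**

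| Girl's status | Section 7.7.1, applied through Sections 4.2, 6, 7.7.2 and Appendix 2 | Appendix 3 |
|---|---|---|
| Prepubertal | No test | No test |
| Pubertal, premenarchal (Tanner Stage 3 named) | Test | No test |
| Post-menarchal | Test | Test |

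The rules differ only in the middle row. Section 7.7.1 does not say whether Tanner Stage 2 counts as pubertal, so the lower edge of that row is open. Appendix 2 does not mention menarche; it conflicts with Appendix 3 only through the Section 7.7.1 definition.

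The serum visits in Appendix 3 (Screening, Baseline, Weeks 48, 72 and 192, and early discontinuation or end of treatment) are the same as those in footnote k. Only the population differs, which points to a drafting slip and not to a deliberately narrower rule.

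**How many tests are at stake per girl**

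The plan gives no figure to reproduce. I counted scheduled pregnancy-test visits in Appendix 2, leaving out Early Discontinuation and Extension visits. The assumption is that the girl is pubertal and premenarchal continuously from Screening to the stated visit.

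- Through Baseline: Screening and Baseline = 2, both serum, both before the first dose.
- Through Week 48: add Weeks 4, 8, 16, 24, 32, 40, 48 (7). 2 + 7 = 9.
- Through Week 96: add Weeks 56, 64, 72, 80, 88, 96 (6). 9 + 6 = 15.
- Through Week 192: add Weeks 108, 120, 132, 144, 156, 168, 180, 192 (8). 15 + 8 = 23.

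The split of the 23 by type depends on the section used:

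- Footnote k: serum at Screening, Baseline and Weeks 48, 72 and 192 = 5; urine 23 − 5 = 18.
- Section 6: serum at Screening, Baseline, Week 48 and Week 192 = 4; urine at the 6 visits of Section 6.2.1 plus the 13 of Section 6.2.3 (which include Week 72) = 19; 4 + 19 = 23.

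The two splits differ because Section 6.2.3 lists a urine test at Week 72 where footnote k has serum. That is a separate discrepancy and does not change the totals.

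**Whether the wider rule can itself be applied at each visit**

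Tanner Staging starts at Baseline, and the Screening examination in Section 6.1.1 excludes breast and urogenital examination. Pubertal stage is therefore not scheduled to be recorded when the Screening test is due. It is recorded at Baseline, where a serum test is also due before dosing. Later staging is every 24 weeks (every 48 in the Extension Phase), so a girl could enter puberty between stagings.

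**The case against.** The strongest reply is that the operative text already has the right rule. Section 6 sends sites to Appendix 2 and to the Section 6 text, and no section in the body refers to Appendix 3. The pre-dose serum test is an eligibility criterion: inclusion criteria are reviewed at Screening, only subjects who meet all of them return for entry, and Section 7.7.2 repeats the requirement. To miss that test, a site would have to let an unreferenced appendix override an inclusion criterion and its own visit lists. Section 6 requires the protocol's blood and urine tests to be run at a central laboratory, but nothing shows that the laboratory's test list was built from Appendix 3. The visit counts describe a schedule and not an expected loss, and the Week 72 and Tanner points are separate matters.

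Most of this stands as a limit on the consequence. Omission is conditional on someone working from Appendix 3, and the laboratory route is a possibility that the documents neither confirm nor exclude. The counts are upper bounds under a stated assumption. Enrollment is also closed (SAP Section 1.3: 90 randomized, 89 treated), so a correction can protect only the remaining on-treatment and Extension visits.

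None of it removes the contradiction. Appendix 3 is part of the protocol, is its list of laboratory assessments, and states a testing population that the protocol's own definition contradicts.

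**Conclusion.** The inconsistency is real and in current text: both Appendix 3 cells exclude premenarchal pubertal girls, whom Section 7.7.1 includes and the rest of the protocol requires to be tested. Confidence in the textual conflict is high. Whether any test was or would be missed cannot be told from the documents.

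Severity is minor. The number of girls affected and the time they spend in that state are not given. Per girl, under the continuity assumption, the tests at stake range from 2 through Baseline to a ceiling of 23 through Week 192. Efficacy, power and the planned analyses are not affected.

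**What to change.** In both pregnancy-test cells of Appendix 3 (serum and urine), replace the post-menarchal restriction with: *Females of childbearing potential only (see Section 7.7.1)*.

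The cost is two wording changes in one appendix, with no test beyond those the body already requires. The change aligns Appendix 3 with the body but does not by itself secure the Screening test, because no Tanner stage is scheduled at that visit. It also leaves the Week 72 serum-or-urine difference between footnote k and Section 6.2.3 unresolved.

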Appendix 4. GSI Grading Scale for Severity of Adverse Events and Laboratory Abnormalities

Antiviral Toxicity Grading Scale Version: 01 April 2015

HEMATOLOGY				
	Grade 1	Grade 2	Grade 3	Grade 4
Hemoglobin HIV POSITIVE Adult and Pediatric ≥ 57 Days	8.5 to 10.0 g/dL 85 to 100 g/L	7.5 to < 8.5 g/dL 75 to < 85 g/L	6.5 to < 7.5 g/dL 65 to < 75 g/L	< 6.5 g/dL < 65 g/L
HIV NEGATIVE Adult and Pediatric ≥ 57 Days	10.0 to 10.9 g/dL 100 to 109 g/L OR Any decrease from Baseline 2.5 to < 3.5 g/dL 25 to < 35 g/L	9.0 to < 10.0 g/dL 90 to < 100 g/L OR Any decrease from Baseline 3.5 to < 4.5 g/dL 35 to < 45 g/L	7.0 to < 9.0 g/dL 70 to < 90 g/L OR Any decrease from Baseline ≥ 4.5 g/dL ≥ 45 g/L	< 7.0 g/dL < 70 g/L
Infant, 36–56 Days (HIV POSITIVE OR NEGATIVE)	8.5 to 9.4 g/dL 85 to 94 g/L	7.0 to < 8.5 g/dL 70 to < 85 g/L	6.0 to < 7.0 g/dL 60 to < 70 g/L	< 6.0 g/dL < 60 g/L
Infant, 22–35 Days (HIV POSITIVE OR NEGATIVE)	9.5 to 10.5 g/dL 95 to 105 g/L	8.0 to < 9.5 g/dL 80 to < 95 g/L	7.0 to < 8.0 g/dL 70 to < 80 g/L	< 7.0 g/dL < 70 g/L
Infant, 1–21 Days (HIV POSITIVE OR NEGATIVE)	12.0 to 13.0 g/dL 120 to 130 g/L	10.0 to < 12.0 g/dL 100 to < 120 g/L	9.0 to < 10.0 g/dL 90 to < 100 g/L	< 9.0 g/dL < 90 g/L

HEMATOLOGY				
	Grade 1	Grade 2	Grade 3	Grade 4
Absolute Neutrophil Count (ANC) Adult and Pediatric, ≥ 7 Months#	1000 to 1300/mm ³ 1.00 to 1.30 GI/L	750 to < 1000/mm ³ 0.75 to < 1.00 GI/L	500 to < 750/mm ³ 0.50 to < 0.75 GI/L	< 500/mm ³ < 0.50 GI/L
Absolute CD4+ Count HIV NEGATIVE ONLY Adult and Pediatric > 13 Years	300 to 400/mm ³ 300 to 400/μL	200 to < 300/mm ³ 200 to < 300/μL	100 to < 200/mm ³ 100 to < 200/μL	< 100/mm ³ < 100/μL
Absolute Lymphocyte Count HIV NEGATIVE ONLY Adult and Pediatric > 13 Years	600 to 650/mm ³ 0.60 to 0.65 GI/L	500 to < 600/mm ³ 0.50 to < 0.60 GI/L	350 to < 500/mm ³ 0.35 to < 0.50 GI/L	< 350/mm ³ < 0.35 GI/L
Platelets	100,000 to < 125,000/mm ³ 100 to < 125 GI/L	50,000 to < 100,000/mm ³ 50 to < 100 GI/L	25,000 to < 50,000/mm ³ 25 to < 50 GI/L	< 25,000/mm ³ < 25 GI/L
WBCs	2000/mm ³ to 2500/mm ³ 2.00 GI/L to 2.50 GI/L	1,500 to < 2,000/mm ³ 1.50 to < 2.00 GI/L	1000 to < 1,500/mm ³ 1.00 to < 1.50 GI/L	< 1000/mm ³ < 1.00 GI/L
Hypofibrinogenemia	100 to 200 mg/dL 1.00 to 2.00 g/L	75 to < 100 mg/dL 0.75 to < 1.00 g/L	50 to < 75 mg/dL 0.50 to < 0.75 g/L	< 50 mg/dL < 0.50 g/L
Hyperfibrinogenemia	> ULN to 600 mg/dL > ULN to 6.0 g/L	> 600 mg/dL > 6.0 g/L	— —	— —
Fibrin Split Product	20 to 40 μg/mL 20 to 40 mg/L	> 40 to 50 μg/mL > 40 to 50 mg/L	> 50 to 60 μg/mL > 50 to 60 mg/L	> 60 μg/mL > 60 mg/L
Prothrombin Time (PT)	> 1.00 to 1.25 × ULN	> 1.25 to 1.50 × ULN	> 1.50 to 3.00 × ULN	> 3.00 × ULN

HEMATOLOGY				
	Grade 1	Grade 2	Grade 3	Grade 4
International Normalized Ratio of prothrombin time (INR)	1.1 to 1.5 x ULN	>1.5 to 2.0 x ULN	>2.0 to 3.0 x ULN	>3.0 x ULN
Activated Partial Thromboplastin Time (APTT)	> 1.00 to 1.66 × ULN	> 1.66 to 2.33 × ULN	> 2.33 to 3.00 × ULN	> 3.00 × ULN
Methemoglobin	5.0 to 10.0%	> 10.0 to 15.0%	> 15.0 to 20.0%	> 20.0%

An overlap between the Grade 1 scale and the Lab's normal range for absolute neutrophils may result for pediatric subjects. Please follow the Gilead convention of grading any result within the LLN and ULN a 0.

CHEMISTRY				
	Grade 1	Grade 2	Grade 3	Grade 4
Hyponatremia	130 to <LLN mEq/L 130 to <LLN mmol/L	125 to < 130 mEq/L 125 to < 130 mmol/L	121 to < 125 mEq/L 121 to < 125 mmol/L	< 121 mEq/L < 121 mmol/L
Hypernatremia	>ULN to 150 mEq/L >ULN to 150 mmol/L	> 150 to 154 mEq/L > 150 to 154 mmol/L	> 154 to 159 mEq/L > 154 to 159 mmol/L	> 159 mEq/L > 159 mmol/L
Hypokalemia Adult and Pediatric ≥ 1 Year	3.0 to <LLN mEq/L 3.0 to <LLN mmol/L	2.5 to < 3.0 mEq/L 2.5 to < 3.0 mmol/L	2.0 to < 2.5 mEq/L 2.0 to < 2.5 mmol/L	< 2.0 mEq/L < 2.0 mmol/L
Infant <1 Year	3.0 to 3.4 mEq/L 3.0 to 3.4 mmol/L	2.5 to < 3.0 mEq/L 2.5 to < 3.0 mmol/L	2.0 to < 2.5 mEq/L 2.0 to < 2.5 mmol/L	< 2.0 mEq/L < 2.0 mmol/L
Hyperkalemia Adult and Pediatric ≥ 1 Year	5.6 to 6.0 mEq/L 5.6 to 6.0 mmol/L	> 6.0 to 6.5 mEq/L > 6.0 to 6.5 mmol/L	> 6.5 to 7.0 mEq/L > 6.5 to 7.0 mmol/L	> 7.0 mEq/L > 7.0 mmol/L
Infant <1 Year	>ULN to 6.0 mEq/L >ULN to 6.0 mmol/L	> 6.0 to 6.5 mEq/L > 6.0 to 6.5 mmol/L	> 6.5 to 7.0 mEq/L > 6.5 to 7.0 mmol/L	> 7.0 mEq/L > 7.0 mmol/L
Hypoglycemia Adult and Pediatric ≥ 1 Month	55 to 64 mg/dL 3.03 to 3.58 mmol/L	40 to < 55 mg/dL 2.20 to < 3.03 mmol/L	30 to < 40 mg/dL 1.64 to < 2.20 mmol/L	< 30 mg/dL < 1.64 mmol/L
Infant, < 1 Month	50 to 54 mg/dL 2.8 to 3.0 mmol/L	40 to < 50 mg/dL 2.2 to < 2.8 mmol/L	30 to < 40 mg/dL 1.7 to < 2.2 mmol/L	< 30 mg/dL < 1.7 mmol/L
Hyperglycemia, Nonfasting	116 to 160 mg/dL 6.42 to 8.91 mmol/L	> 160 to 250 mg/dL > 8.91 to 13.90 mmol/L	> 250 to 500 mg/dL > 13.90 to 27.79 mmol/L	> 500 mg/dL > 27.79 mmol/L

CHEMISTRY				
	Grade 1	Grade 2	Grade 3	Grade 4
Hyperglycemia, Fasting	110 to 125 mg/dL 6.08 to 6.96 mmol/L	>125 to 250 mg/dL >6.96 to 13.90 mmol/L	>250 to 500 mg/dL >13.90 to 27.79 mmol/L	>500 mg/dL >27.79 mmol/L
Hypocalcemia (corrected for albumin if appropriate*) Adult and Pediatric ≥2 Years	7.8 <LLN mg/dL 1.94 to <LLN mmol/L	7.0 to < 7.8 mg/dL 1.74 to < 1.94 mmol/L	6.1 to < 7.0 mg/dL 1.51 to < 1.74 mmol/L	< 6.1 mg/dL < 1.51 mmol/L
Pediatric ≥7 days -2 Years	7.8 to 8.4 mg/dL 1.94 to 2.10 mmol/L	7.0 to <7.8 mg/dL 1.74 to <1.94 mmol/L	6.1 to <7.0 mg/dL 1.51 to < 1.74 mmol/L	< 6.1 mg/dL < 1.51 mmol/L
Infant, < 7 Days	6.5 to 7.5 mg/dL 1.61 to 1.88 mmol/L	6.0 to < 6.5 mg/dL 1.49 to < 1.61 mmol/L	5.5 to < 6.0 mg/dL 1.36 to < 1.49 mmol/L	< 5.5 mg/dL < 1.36 mmol/L
Hypercalcemia (corrected for albumin if appropriate*) Adult and Pediatric ≥ 7 Days	>ULN to 11.5 mg/dL >ULN to 2.88 mmol/L	> 11.5 to 12.5 mg/dL > 2.88 to 3.13 mmol/L	> 12.5 to 13.5 mg/dL > 3.13 to 3.38 mmol/L	> 13.5 mg/dL > 3.38 mmol/L
Infant, < 7 Days	11.5 to 12.4 mg/dL 2.86 to 3.10 mmol/L	> 12.4 to 12.9 mg/dL > 3.10 to 3.23 mmol/L	> 12.9 to 13.5 mg/dL > 3.23 to 3.38 mmol/L	> 13.5 mg/dL > 3.38 mmol/L
Hypocalcemia (ionized)	3.0 mg/dL to < LLN 0.74 mmol/L to < LLN	2.5 to < 3.0 mg/dL 0.62 to < 0.74 mmol/L	2.0 to < 2.5 mg/dL 0.49 to < 0.62 mmol/L	< 2.0 mg/dL < 0.49 mmol/L
Hypercalcemia (ionized)	> ULN to 6.0 mg/dL > ULN to 1.50 mmol/L	> 6.0 to 6.5 mg/dL > 1.50 to 1.63 mmol/L	> 6.5 to 7.0 mg/dL > 1.63 to 1.75 mmol/L	> 7.0 mg/dL > 1.75 mmol/L
Hypomagnesemia	1.40 to <LLN mg/dL 1.2 to <LLN mEq/L 0.58 to <LLN mmol/L	1.04 to < 1.40 mg/dL 0.9 to < 1.2 mEq/L 0.43 to < 0.58 mmol/L	0.67 to < 1.04 mg/dL 0.6 to < 0.9 mEq/L 0.28 to < 0.43 mmol/L	< 0.67 mg/dL < 0.6 mEq/L < 0.28 mmol/L

CHEMISTRY				
	Grade 1	Grade 2	Grade 3	Grade 4
Hypophosphatemia Adult and Pediatric > 14 Years	2.0 to < LLN mg/dL 0.63 to < LLN mmol/L	1.5 to < 2.0 mg/dL 0.47 to < 0.63 mmol/L	1.0 to < 1.5 mg/dL 0.31 to < 0.47 mmol/L	< 1.0 mg/dL < 0.31 mmol/L
Pediatric 1 Year–14 Years	3.0 to < LLN mg/dL 0.96 to < LLN mmol/L	2.5 to < 3.0 mg/dL 0.80 to < 0.96 mmol/L	1.5 to < 2.5 mg/dL 0.47 to < 0.80 mmol/L	< 1.5 mg/dL < 0.47 mmol/L
Pediatric < 1 Year	3.5 to < LLN mg/dL 1.12 to < LLN mmol/L	2.5 to < 3.5 mg/dL 0.80 to < 1.12 mmol/L	1.5 to < 2.5 mg/dL 0.47 to < 0.80 mmol/L	< 1.5 mg/dL < 0.47 mmol/L
Hyperbilirubinemia Adult and Pediatric > 14 Days	> 1.0 to 1.5 × ULN	> 1.5 to 2.5 × ULN	> 2.5 to 5.0 × ULN	> 5.0 × ULN
Infant, ≤ 14 Days (non-hemolytic)	NA	20.0 to 25.0 mg/dL 342 to 428 μmol/L	> 25.0 to 30.0 mg/dL > 428 to 513 μmol/L	> 30.0 mg/dL > 513 μmol/L
Infant, ≤ 14 Days (hemolytic)	NA	NA	20.0 to 25.0 mg/dL 342 to 428 μmol/L	> 25.0 mg/dL > 428 μmol/L
Blood Urea Nitrogen	1.25 to 2.50 × ULN	> 2.50 to 5.00 × ULN	> 5.00 to 10.00 × ULN	> 10.00 × ULN
Hyperuricemia	> ULN to 10.0 mg/dL > ULN to 597 μmol/L	> 10.0 to 12.0 mg/dL > 597 to 716 μmol/L	> 12.0 to 15.0 mg/dL > 716 to 895 μmol/L	> 15.0 mg/dL > 895 μmol/L

CHEMISTRY				
	Grade 1	Grade 2	Grade 3	Grade 4
Hypouricemia Adult and Pediatric ≥ 1 year	1.5 mg/dL to < LLN 87 μmol/L to < LLN	1.0 to < 1.5 mg/dL 57 to < 87 μmol/L	0.5 to < 1.0 mg/dL 27 to < 57 μmol/L	< 0.5 mg/dL < 27 μmol/L
Infant < 1 Year	N/A	1.0 mg/dl to <LLN- 57 μmol to <LLN	0.5 to < 1.0 mg/dL 27 to < 57 μmol/L	< 0.5 mg/dL < 27 μmol/L
Creatinine**	> 1.50 to 2.00 mg/dL > 133 to 177 μmol/L	> 2.00 to 3.00 mg/dL > 177 to 265 μmol/L	> 3.00 to 6.00 mg/dL > 265 to 530 μmol/L	> 6.00 mg/dL > 530 μmol/L
Bicarbonate Adult and Pediatric ≥ 4 Years	16.0 mEq/L to < LLN 16.0 mmol/L to < LLN	11.0 to < 16.0 mEq/L 11.0 to < 16.0 mmol/L	8.0 to < 11.0 mEq/L 8.0 to < 11.0 mmol/L	< 8.0 mEq/L < 8.0 mmol/L
Pediatric < 4 Years	NA	11.0 mEq/Lto <LLN 11.0 mmol/L to <LLN	8.0 to < 11.0 mEq/L 8.0 to < 11.0 mmol/L	< 8.0 mEq/L < 8.0 mmol/L
Triglycerides (Fasting)	NA	500 to 750 mg/dL 5.64–8.47 mmol/L	> 750 to 1200 mg/dL > 8.47–13.55 mmol/L	> 1200 mg/dL > 13.55 mmol/L
LDL (Fasting) Adult	130 to 160 mg/dL 3.35 to 4.15 mmol/L	>160 to 190 mg/dL >4.15 to 4.92 mmol/L	> 190 mg/dL >4.92 mmol/L	NA
LDL (Fasting) Pediatric >2 to <18 years	110 to 130 mg/dL 2.84 to 3.37 mmol/L	>130 to 190 mg/dL >3.37 to 4.92 mmol/L	> 190 mg/dL >4.92 mmol/L	NA

CHEMISTRY				
	Grade 1	Grade 2	Grade 3	Grade 4
Hypercholesterolemia (Fasting)	200 to 239 mg/dL	> 239 to 300 mg/dL	> 300 mg/dL	NA
	5.16 to 6.19 mmol/L	> 6.19 to 7.77 mmol/L	> 7.77 mmol/L	
Pediatric < 18 Years	170 to 199 mg/dL 4.39 to 5.15 mmol/L	> 199 to 300 mg/dL > 5.15 to 7.77 mmol/L	> 300 mg/dL > 7.77 mmol/L	NA
Creatine Kinase	3.0 to < 6.0 × ULN	6.0 to < 10.0 × ULN	10.0 to < 20.0 × ULN	≥ 20.0 × ULN

*Calcium should be corrected for albumin if albumin is < 4.0 g/dL

** An overlap between the Grade 1 scale and the Lab's normal range for creatinine may result for Male subjects >70 yrs. Please follow the Gilead convention of grading any result within the LLN and ULN a 0.

ENZYMES				
	Grade 1	Grade 2	Grade 3	Grade 4
AST (SGOT)	1.25 to 2.50 × ULN	> 2.50 to 5.00 × ULN	> 5.00 to 10.00 × ULN	> 10.00 × ULN
ALT (SGPT)	1.25 to 2.50 × ULN	> 2.50 to 5.00 × ULN	> 5.00 to 10.00 × ULN	> 10.00 × ULN
GGT	1.25 to 2.50 × ULN	> 2.50 to 5.00 × ULN	> 5.00 to 10.00 × ULN	> 10.00 × ULN
Alkaline Phosphatase	1.25 to 2.50 × ULN	> 2.50 to 5.00 × ULN	> 5.00 to 10.00 × ULN	> 10.00 × ULN
Total Amylase	> 1.0 to 1.5 × ULN	> 1.5 to 2.0 × ULN	> 2.0 to 5.0 × ULN	> 5.0 × ULN
Pancreatic Amylase	> 1.0 to 1.5 × ULN	> 1.5 to 2.0 × ULN	> 2.0 to 5.0 × ULN	> 5.0 × ULN
Lipase	> 1.0 to 1.5 × ULN	> 1.5 to 3.0 × ULN	> 3.0 to 5.0 × ULN	> 5.0 × ULN
Albumin	-	2.0 to < LLN g/dL 20 to < LLN g/L	< 2.0 g/dL < 20 g/L	NA
Pediatrics <16 years				
≥ 16 years	3.0 g/dL to < LLN 30 g/L to < LLN	2.0 to < 3.0 g/dL 20 to < 30 g/L	< 2.0 g/dL < 20 g/L	NA

URINALYSIS				
	Grade 1	Grade 2	Grade 3	Grade 4
Hematuria (Dipstick)	1+	2+	3-4+	NA
Hematuria (Quantitative) See Note below				
Females	>ULN - 10 RBC/HPF	> 10-75 RBC/HPF	> 75 RBC/HPF	NA
Males	6-10 RBC/HPF	> 10-75 RBC/HPF	> 75 RBC/HPF	NA
Proteinuria (Dipstick)	1+	2-3+	4+	NA
Proteinuria, 24 Hour Collection				
Adult and Pediatric ≥ 10 Years	200 to 999 mg/24 h	>999 to 1999 mg/24 h	>1999 to 3500 mg/24 h	> 3500 mg/24 h
Pediatric > 3 Mo to < 10 Years	201 to 499 mg/m ² /24 h	>499 to 799 mg/m ² /24 h	>799 to 1000 mg/m ² /24 h	> 1000 mg/ m ² /24 h
Glycosuria (Dipstick)	1+	2-3+	4+	NA

Notes:

- Toxicity grades for Quantitative and Dipstick Hematuria will be assigned by Covance Laboratory, however for other laboratories, toxicity grades will only be assigned to Dipstick Hematuria.
- With the exception of lipid tests, any graded laboratory test with a result that is between the LLN and ULN should be assigned Grade 0.
- If the severity of a clinical AE could fall under either one of two grades (e.g., the severity of an AE could be either Grade 2 or Grade 3), select the higher of the two grades for the AE.

CARDIOVASCULAR				
	Grade 1	Grade 2	Grade 3	Grade 4
Cardiac Arrhythmia (general) (By ECG or physical exam)	Asymptomatic AND No intervention indicated	Asymptomatic AND Non-urgent medical intervention indicated	Symptomatic, non-life-threatening AND Non-urgent medical intervention indicated	Life-threatening arrhythmia OR Urgent intervention indicated
Cardiac-ischemia/Infarction	NA	NA	Symptomatic ischemia (stable angina) OR Testing consistent with ischemia	Unstable angina OR Acute myocardial infarction
Hemorrhage (significant acute blood loss)	NA	Symptomatic AND No transfusion indicated	Symptomatic AND Transfusion of ≤ 2 units packed RBCs (for children ≤ 10 cc/kg) indicated	Life-threatening hypotension OR Transfusion of > 2 units packed RBCs indicated (for children ≤ 10 cc/kg) indicated
Hypertension (with repeat testing at same visit)	140–159 mmHg systolic OR 90–99 mmHg diastolic	> 159–179 mmHg systolic OR > 99–109 mmHg diastolic	> 179 mmHg systolic OR > 109 mmHg diastolic	Life-threatening consequences (eg, malignant hypertension) OR Hospitalization (other than ER visit) indicated
Pediatric ≤ 17 Years (with repeat testing at same visit)	NA	91st–94th percentile adjusted for age, height, and gender (systolic and/or diastolic)	≥ 95th percentile adjusted for age, height, and gender (systolic and/or diastolic)	Life-threatening consequences (eg, malignant hypertension) OR Hospitalization indicated (other than emergency room visit)
Hypotension	NA	Symptomatic, corrected with oral fluid replacement	Symptomatic, IV fluids indicated	Shock requiring use of vasopressors or mechanical assistance to maintain blood pressure
Pericardial Effusion	Asymptomatic, small effusion requiring no intervention	Asymptomatic, moderate or larger effusion requiring no intervention	Effusion with non-life-threatening physiologic consequences OR Effusion with nonurgent intervention indicated	Life-threatening consequences (eg, tamponade) OR Urgent intervention indicated

CARDIOVASCULAR				
	Grade 1	Grade 2	Grade 3	Grade 4
Prolonged PR Interval	PR interval 0.21 to 0.25 sec	PR interval > 0.25 sec	Type II 2nd degree AV block OR Ventricular pause > 3.0 sec	Complete AV block
Pediatric ≤ 16 Years	1st degree AV block (PR > normal for age and rate)	Type I 2nd degree AV block	Type II 2nd degree AV block	Complete AV block
Prolonged QTc	Asymptomatic, QTc interval 0.45 to 0.47 sec OR Increase interval < 0.03 sec above baseline	Asymptomatic, QTc interval 0.48 to 0.49 sec OR Increase in interval 0.03 to 0.05 sec above baseline	Asymptomatic, QTc interval ≥ 0.50 sec OR Increase in interval ≥ 0.06 sec above baseline	Life-threatening consequences, eg, Torsade de pointes or other associated serious ventricular dysrhythmia
Pediatric ≤ 16 Years	Asymptomatic, QTc interval 0.450 to 0.464 sec	Asymptomatic, QTc interval 0.465 to 0.479 sec	Asymptomatic, QTc interval ≥ 0.480 sec	Life-threatening consequences, eg, Torsade de pointes or other associated serious ventricular dysrhythmia
Thrombosis/Embolism	NA	Deep vein thrombosis AND No intervention indicated (eg, anticoagulation, lysis filter, invasive procedure)	Deep vein thrombosis AND Intervention indicated (eg, anticoagulation, lysis filter, invasive procedure)	Embolic event (eg, pulmonary embolism, life-threatening thrombus)
Vasovagal Episode (associated with a procedure of any kind)	Present without loss of consciousness	Present with transient loss of consciousness	NA	NA
Ventricular Dysfunction (congestive heart failure, CHF)	NA	Asymptomatic diagnostic finding AND intervention indicated	New onset with symptoms OR Worsening symptomatic CHF	Life-threatening CHF

RESPIRATORY				
	Grade 1	Grade 2	Grade 3	Grade 4
Bronchospasm (acute)	FEV1 or peak flow reduced to 70% to 80%	FEV1 or peak flow 50% to 69%	FEV1 or peak flow 25% to 49%	Cyanosis OR FEV1 or peak flow < 25% OR Intubation
Dyspnea or Respiratory Distress	Dyspnea on exertion with no or minimal interference with usual social & functional activities	Dyspnea on exertion causing greater than minimal interference with usual social & functional activities	Dyspnea at rest causing inability to perform usual social & functional activities	Respiratory failure with ventilatory support indicated
Pediatric < 14 Years	Wheezing OR minimal increase in respiratory rate for age	Nasal flaring OR Intercostal retractions OR Pulse oximetry 90% to 95%	Dyspnea at rest causing inability to perform usual social & functional activities OR Pulse oximetry < 90%	Respiratory failure with ventilatory support indicated

OCULAR/VISUAL				
	Grade 1	Grade 2	Grade 3	Grade 4
Uveitis	Asymptomatic but detectable on exam	Symptomatic anterior uveitis OR Medical intervention indicated	Posterior or pan-uveitis OR Operative intervention indicated	Disabling visual loss in affected eye(s)
Visual Changes (from baseline)	Visual changes causing no or minimal interference with usual social & functional activities	Visual changes causing greater than minimal interference with usual social & functional activities	Visual changes causing inability to perform usual social & functional activities	Disabling visual loss in affected eye(s)

SKIN				
	Grade 1	Grade 2	Grade 3	Grade 4
Alopecia	Thinning detectable by study participant or caregiver (for disabled adults)	Thinning or patchy hair loss detectable by health care provider	Complete hair loss	NA
Cutaneous Reaction – Rash	Localized macular rash	Diffuse macular, maculopapular, or morbilliform rash OR Target lesions	Diffuse macular, maculopapular, or morbilliform rash with vesicles or limited number of bullae OR Superficial ulcerations of mucous membrane limited to one site	Extensive or generalized bullous lesions OR Stevens-Johnson syndrome OR Ulceration of mucous membrane involving two or more distinct mucosal sites OR Toxic epidermal necrolysis (TEN)
Hyperpigmentation	Slight or localized	Marked or generalized	NA	NA
Hypopigmentation	Slight or localized	Marked or generalized	NA	NA
Pruritis (itching – no skin lesions) (See also Injection Site Reactions: Pruritis associated with injection)	Itching causing no or minimal interference with usual social & functional activities	Itching causing greater than minimal interference with usual social & functional activities	Itching causing inability to perform usual social & functional activities	NA

GASTROINTESTINAL				
	Grade 1	Grade 2	Grade 3	Grade 4
Anorexia	Loss of appetite without decreased oral intake	Loss of appetite associated with decreased oral intake without significant weight loss	Loss of appetite associated with significant weight loss	Life-threatening consequences OR Aggressive intervention indicated [eg, tube feeding or total parenteral nutrition]
Ascites	Asymptomatic	Symptomatic AND Intervention indicated (eg, diuretics or therapeutic paracentesis)	Symptomatic despite intervention	Life-threatening consequences
Cholecystitis	NA	Symptomatic AND Medical intervention indicated	Radiologic, endoscopic, or operative intervention indicated	Life-threatening consequences (eg, sepsis or perforation)
Constipation	NA	Persistent constipation requiring regular use of dietary modifications, laxatives, or enemas	Obstipation with manual evacuation indicated	Life-threatening consequences (eg, obstruction)
